### **7.4. Participant with Only Patient-reported Data**

If consent and medical release(s) are provided by the participant, the surveillance program will attempt to obtain HCP confirmation of all patient-reported data, including data provided by the participant at self-enrollment. Participants with only patient-reported data will be excluded from the analysis population, and patient-reported data without HCP confirmation will be summarized separately in the reports (see Section 9.2.1 and Section 9.2.2).

### **7.5. Subsequent Pregnancies**

Individuals who have previously enrolled in the surveillance program with a prior pregnancy will be eligible to enroll in the surveillance program with subsequent pregnancies. Each pregnancy will be assigned a separate participant identification (ID) number, and the number of subsequent pregnancies will be enumerated in the reports.

### **7.6. Multiple Gestation Pregnancies**

Multiple gestation pregnancies will be enrolled in the surveillance program and included in the analysis population; however, for the analyses of preterm birth, SGA, and postnatal growth

deficiency, multiple gestation pregnancies will be excluded from the analysis population due to the higher risk of these outcomes in twins and higher-order multiples (see Section 9.2.2.1).

### 7.7. Analysis Population

Individuals will be excluded from the analysis population if they are duplicate reports (invalid), they lack the minimum criteria for enrollment (invalid), the outcome of their pregnancy occurred prior to first contact with the surveillance program (retrospectively enrolled participants and participants exposed during lactation only), or if data are not confirmed by an HCP (participants with only patient-reported data). Participants with identifiable and non-identifiable data will be included in the analysis population if pregnancy outcome data are collected (i.e., the participant is not lost to follow-up).

[figure not shown]
In summary, the analysis population will include participants who:

- Are valid
- Are prospectively enrolled and were not exposed during lactation only
- Have HCP confirmation of data
- Are not considered lost to follow-up

For the analyses of preterm birth, SGA, and postnatal growth deficiency, multiple gestation pregnancies will additionally be excluded from the analysis population (see Figure 1).

Retrospectively enrolled participants, participants exposed during lactation only, and participants with only patient-reported data will be included in supplementary analyses.

**Figure 1. Summary of Analysis Population**

HCP = healthcare provider.

## **8. DEFINITIONS OF VARIABLES**

### **8.1. Exposure Definitions and Ascertainment**

Exposure to omaveloxolone is a condition for enrollment. Exposure is defined as bodily uptake of at least 1 dose of omaveloxolone at any time during pregnancy (from conception to pregnancy outcome), prior to pregnancy (within a specified time based on the product's half-life), or during lactation. Due to the 57-hour half-life of omaveloxolone, participants will be considered exposed during pregnancy if a dose is taken within 12 days (5 half-lives) prior to conception. Participants will be considered exposed during lactation if a dose is taken at any time during lactation.

Detailed information on dose, route, frequency, dates/duration of exposure, and indication/reason for use will be collected, and exposure will be further categorized by earliest trimester of exposure. For information on the methods used to determine gestational age and trimester of exposure, refer to Section 8.3. Exposure information will be updated at each pregnancy and infant follow-up.

### **8.2. Outcome Definitions and Ascertainment**

Table 2 presents the definitions of the outcomes. For outcomes not simply reported by the HCP, additional information on outcome ascertainment is provided.

**Table 2. Outcome Definitions and Ascertainment**

| Outcome                             | Definition  | Ascertainment   |
|-------------------------------------|---|---|
| Major congenital malformation (MCM) | An abnormality of body structure or function that is present at birth; is of prenatal origin (i.e., birth defect); has significant medical, social, or cosmetic consequences for the affected individual; and typically requires medical intervention [Centers for Disease Control and Prevention (CDC) 2020]               | 
The surveillance program defines and codes MCMs with criteria specified by CDC MACDP [Centers for Disease Control and Prevention (CDC) 2021]. If participants who reside in Europe are enrolled, MCMs will also be defined and coded using the criteria specified by EUROCAT [EUROCAT 2021]; APPENDIX A).
 
Exclusion criteria for analyses: To avoid misattribution of the malformation to the medication, MCMs not known to be associated with medication exposure, such as chromosomal abnormalities, genetic syndromes, prematurity-related conditions in infants born at <36 gestational weeks (e.g., patent ductus arteriosus, patent foramen ovale, inguinal hernias, or undescended testes), and positional effects (e.g., hip dislocation due to breech position or abnormal skull shape due to crowding by multiple fetuses), will not be considered MCMs in the statistical analyses [Holmes and Westgate 2011].
 
Adjudication process: An independent expert in clinical genetics and neonatology who is blinded to exposure will review all malformations reported from any source and classify them using the CDC’s MACDP system (and EUROCAT, if applicable). Additionally, the birth defect evaluator will provide the organ system involved, etiology of the defect (e.g., chromosomal abnormality, prematurity), and approximate timing of the development of observed defects. Then the birth defect evaluator will be unblinded to exposure and assess the possible temporal association between exposure (to omaveloxolone) and the development of the observed defects. If additional information is needed to aid in classification, the birth defect evaluator will request additional information using the targeted follow-up process outlined in Section 6.1.3. This evaluation will occur soon after the malformation is reported. Additional reviews will occur if new information is received for the case. The Sponsor will not be involved in any activities related to case review or adjudication.
 |
| Minor congenital malformation       | An anomaly or abnormality of body structure that is present at birth, is of prenatal origin (i.e., birth defect), poses no significant health problem in the neonatal period, and tends to have limited social or cosmetic consequences for the affected individual [Centers for Disease Control and Prevention (CDC) 2020] | 
The surveillance program defines and codes minor congenital malformations with criteria specified as defined by CDC [Centers for Disease Control and Prevention (CDC) 2019]. The same process for adjudicating MCMs will be used to adjudicate minor congenital malformations.
   |

| Outcome                          | Definition  | Ascertainment  |
|----------------------------------|---|--|
| Gestational diabetes             | Any degree of glucose intolerance with onset or first recognition during pregnancy [ American Diabetes Association 2004 ]   | -  |
| Preeclampsia                     | High blood pressure and signs of liver or kidney damage (e.g., proteinuria) occurring at >20 gestational weeks [ ACOG Committee on Practice Bulletins--Obstetrics 2002 ]  | -  |
| Fetal loss                       | A fetal loss that occurs for any reason at any time during pregnancy  | -  |
| Spontaneous abortion (SAB)       | An involuntary fetal loss or the expulsion of the products of conception occurring at <20 gestational weeks   | Section 8.3 provides information on the methods used to calculate gestational age. |
| Stillbirth                       | As defined by the ACOG, an involuntary fetal loss occurring at $\geq 20$ gestational weeks or, if gestational age is unknown, a fetus weighing $\geq 350$ g [ American College of Obstetricians and Gynecologists (ACOG) 2020 ] | Section 8.3 provides information on the methods used to calculate gestational age. |
| Elective or therapeutic abortion | A voluntary fetal loss or interruption of pregnancy that occurs for any reason, including but not limited to for the preservation of maternal health or due to fetal abnormalities  | -  |
| Fetal loss, type not specified   | A fetal loss that is not reported as SAB, stillbirth, or elective therapeutic abortion  | -  |
| Live birth                       | The birth of a living fetus at $\geq 20$ gestational weeks or, if gestational age is unknown, weighing $\geq 350$ g   | -  |
| Preterm birth                    | A live birth occurring at <37 gestational weeks   | Section 8.3 provides information on the methods used to calculate gestational age. |

| Outcome                                       | Definition   | Ascertainment  |
|---|--|--|
| Small for gestational age (SGA)               | Birth weight <10 th percentile for sex and gestational age using standard growth charts for full and preterm live-born infants [Battaglia and Lubchenco 1967]   | For the determination of SGA, the surveillance program will utilize the sex-specific international growth reference standards from the INTERGROWTH-21 st for those born between 24 0/7 and 42 6/7 gestational weeks [Villar 2014; Villar 2016]. The INTERGROWTH-21 st standards are the latest available global reference standards, representing contemporary information from an international, multiethnic, diverse population, and have been specifically developed for modern research.   |
| Neonatal death                                | Death of a live-born infant within the first 28 days of life   | -  |
| Infant death                                  | Death of a live-born infant within first year of life  | -  |
| Postnatal growth deficiency                   | Weight, length, or head circumference in <10 th percentile for sex and age using standard growth charts   | Postnatal growth deficiency will be evaluated at approximately 4 months and 1 year of infant age; deficiencies in weight, length, and head circumference will be evaluated separately. For the determination of postnatal growth deficiency, the surveillance program will utilize the sex-specific international growth reference standards from the World Health Organization (WHO) for children ages 0 to 59 months. The WHO growth standards are recommended for use in the US for infants and children 0 to 2 years of age [Centers for Disease Control and Prevention (CDC) 2010]. |

### 8.3. Other Variable Definitions and Ascertainment

Per the American College of Obstetricians and Gynecologists (ACOG), gestational age and the EDD should be determined by the obstetric HCP as soon as data are obtained on the LMP, first accurate ultrasound, or both. ACOG considers ultrasound measurement of the embryo or fetus in the first trimester (up to and including 136/7 gestational weeks) the most accurate method to establish or confirm gestational age and discourages against changing the EDD based on subsequent ultrasounds. Any pregnancy without an ultrasound before 220/7 gestational weeks to confirm or revise the EDD should be considered sub-optimally dated. If the pregnancy resulted from ART, the obstetric HCP should use ART-derived gestational age (e.g., based on age of embryo and date of transfer) to determine EDD. ACOG further recommends that the best estimate of EDD by the obstetric HCP, rather than estimates based on LMP alone, be used for research purposes [[American College of Obstetricians and Gynecologists \(ACOG\) 2017](#)].

Based on ACOG's recommendations, the surveillance program will attempt to collect the EDD from the obstetric HCP and determine whether the EDD was calculated based on LMP, ultrasound, or ART data. If ultrasound-based, whether the ultrasound was performed before 140/7, before 220/7, or at 220/7 gestational weeks or later will also be collected. For prospectively enrolled participants, EDD data will be collected at each data collection timepoint throughout pregnancy. If a corrected EDD is reported on a subsequent form that is different from the EDD initially reported, the surveillance program will evaluate whether a correction is appropriate, based on the timing of the correction and the methods used to determine the corrected EDD, and follow-up with the reporter, if needed.

The surveillance program will conform to ACOG recommendations for determining the "best" EDD, and EDD will be used to calculate gestational age. Based on EDD, the first day of LMP and date of conception (DOC) will be calculated as follows:

- First day of LMP, defined as 00/7 gestational week, will be calculated as EDD minus 280 days (40 weeks)
- DOC, defined as 20/7 gestational weeks, will be calculated as first day of LMP plus 14 days (2 weeks)

If EDD is not reported by the HCP but LMP data are available, the surveillance program will use the first day of LMP to calculate EDD, gestational age, and DOC.

Gestational age will be calculated as the number of weeks elapsed since the first day of LMP.

- Gestational weeks 00/7 to 136/7 will be considered the first trimester
- Gestational weeks 140/7 to 276/7 will be considered the second trimester
- Gestational weeks 280/7 to pregnancy outcome will be considered the third trimester

## **9. STATISTICAL METHODS AND SAMPLE SIZE**

### **9.1. Sample Size**

All eligible individuals meeting the enrollment criteria will be considered for enrollment into the single-arm, observational pregnancy safety study. As FA is a rare condition, and the USPI and patient package insert advise against using omaveloxolone during pregnancy or breastfeeding, approximately 10 to 20 individuals are anticipated to enroll during the study period.

### **9.2. Methods of Analysis**

This study is observational, and epidemiologic methods will be employed for data collection and analyses. Analyses will be conducted in accordance with the study objectives and applicable guidelines.

Study data will be summarized in tables and listings, as appropriate (see Section 9.2.1 and Section 9.2.2 for more details). These data include maternal demographic characteristics and pre-pregnancy anthropometrics, pregnancy information, maternal obstetrical history, family history of congenital malformations, disease information, maternal exposures during pregnancy, pregnancy outcome information (including gestational age of outcome), maternal lactation information and exposures during lactation (if applicable), and infant outcome information. For each continuous variable, the number of observations, median, mean, standard deviation, interquartile range, minimum, and maximum will be reported. For each categorical variable, the frequency and percentage in each category will be reported. The frequency and percentage of participants with missing data for each data point will be presented. Results will be rounded to 1 decimal place; therefore, percentages may not always add up to 100.

Data analyses will be performed with SAS® statistical software (version 9.4 or higher, SAS Institute, Cary, NC).

#### **9.2.1. Demographic and Baseline Characteristics**

Demographic and baseline characteristics will be summarized with simple descriptive statistics and presented in tables and listings. Demographic and baseline characteristics will be summarized for the entire enrolled population cumulatively and stratified by the following sub-populations, which are not mutually exclusive:

- Analysis population (see Section 7.7)
- Participants prospectively enrolled in the lactation only study
- Retrospectively enrolled participants
- Prospectively enrolled participants lost to follow-up
- Participants with only patient-reported data

For the calculation of MCM prevalence rate, live births and stillbirths will be included in the numerator, and only live births will be included in the denominator. The MACDP calculates rates by this convention, which increases sensitivity [Correa 2007]. In the primary analysis, MCMs not associated with medication exposure will be included in the numerator; in the secondary analysis, they will be excluded.

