***Pregnancy Outcome Information***

- Pregnancy outcome, classified in 1 of the following mutually exclusive categories: fetal loss (SAB, stillbirth, elective or therapeutic abortion, or fetal loss, type not specified) or live birth
- Date of pregnancy outcome
- Gestational age at pregnancy outcome
- Fetal/infant sex

- Fetal/infant weight, length, and head circumference at pregnancy outcome
- Route of delivery (i.e., spontaneous vaginal delivery, assisted vaginal delivery, or cesarean delivery)
- Congenital malformations (major and minor) and assessment of potential contributing factors
- For a noninduced fetal loss (SAB, stillbirth), factors that may have had an impact on the fetal loss and attribution (e.g., incompetent cervix, previous fetal loss)
- For elective or therapeutic abortion, reason (e.g., finding on prenatal test, risk to mother's health, undesired pregnancy)

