### **7.2. Prospectively Enrolled Versus Retrospectively Enrolled Participants**

The surveillance program will encourage prospective enrollment; however, retrospective enrollment in the surveillance program will be permitted. For participants exposed to omaveloxolone during both pregnancy and lactation, a prospectively enrolled participant is defined as an individual who is enrolled or for whom initial contact with the surveillance program is made prior to pregnancy outcome. For participants exposed during lactation only, data will be reported separately from pregnancy exposure cases and a prospectively enrolled participant is defined as an individual who is enrolled prior to the start of breastfeeding. For participants exposed to omaveloxolone during both pregnancy and lactation, a retrospectively enrolled participant is defined as an individual who is enrolled or for whom initial contact with the surveillance program is made after the pregnancy outcome has occurred. For participants exposed during lactation only, data will be reported separately from pregnancy exposure cases and a retrospectively enrolled participant is defined as an individual who is enrolled following the start of breastfeeding. Retrospectively enrolled participants can be biased toward the reporting of more unusual and severe outcomes and are less likely to be representative of the general population than prospectively enrolled participants. Retrospectively enrolled participants and participants exposed during lactation only will be excluded from the analysis population and summarized separately in reports (see Section 9.2.1 and Section 9.2.2).

Diagnostic prenatal tests (e.g., ultrasound to scan for structural defects at approximately 20 gestational weeks, chorionic villus sampling, and amniocentesis) can determine with high accuracy whether a fetus has a structural or chromosomal abnormality. If the results of

diagnostic prenatal testing are known prior to enrollment or first contact with the surveillance program, regardless of the results, the individual will be considered prospectively enrolled. However, this practice may introduce bias due to knowledge or perceived knowledge (through diagnostic prenatal testing) of the pregnancy outcome [Gliklich 2020; Kennedy 2004]. If the sample size allows, 3 groups of prospectively enrolled participants will be examined in supplementary analyses:

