**Table 3. Calculation of Outcome Prevalence**

| Outcome                        | Numerator  | Denominator   |
|--------------------------------|--|---|
| Primary analysis        | Live births and stillbirths with confirmed MCMs ( including MCMs not associated with medication exposure) among individuals with pregnancy outcome data and exposure during the first trimester | Live births among individuals with pregnancy outcome data and exposure during the first trimester |
| Secondary analysis      | Live births and stillbirths with confirmed MCMs ( excluding MCMs not associated with medication exposure) among individuals with pregnancy outcome data and exposure during the first trimester | Live births among individuals with pregnancy outcome data and exposure during the first trimester |
| Minor congenital malformations | Live births with minor congenital malformations among individuals with pregnancy outcome data  | Live births among individuals with pregnancy outcome data   |
| Gestational diabetes           | Gestational diabetes among individuals with pregnancy outcome data   | Individuals with pregnancy outcome data   |
| Preeclampsia                   | Pre-eclampsia among individuals with pregnancy outcome data  | Individuals with pregnancy outcome data   |

| Outcome   | Numerator   | Denominator  |
|--|--|---|
| Fetal loss   | Fetal losses, including SABs, stillbirths, elective or therapeutic abortions, and losses with unknown type, among individuals with pregnancy outcome data                          | Individuals with pregnancy outcome data   |
| SAB  | SABs among individuals with pregnancy outcome data who are enrolled and exposed prior to 20 gestational weeks  | Individuals with pregnancy outcome data who are enrolled and exposed prior to 20 gestational weeks  |
| Stillbirth   | Stillbirths among individuals with pregnancy outcome data  | Live births and stillbirths among individuals with pregnancy outcome data   |
| Elective or therapeutic abortion                                   | Elective or therapeutic abortions among individuals with pregnancy outcome data  | Live births among individuals with pregnancy outcome data   |

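### Table 3 leaves confirmed MCMs in abortions and miscarriages out of both MCM analyses, and divides elective or therapeutic abortions by live births

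*Protocol*

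**What the plan says.** Section 9.2.2.1 states the MCM rule: "live births and stillbirths will be included in the numerator, and only live births will be included in the denominator". It gives a reason: "The MACDP calculates rates by this convention, which increases sensitivity". Table 3 repeats the rule. The numerator is "Live births and stillbirths with confirmed MCMs" and the denominator is "Live births among individuals with pregnancy outcome data and exposure during the first trimester". The primary and secondary analyses differ only in whether MCMs not associated with medication are counted; neither counts an MCM in an abortion or an SAB. Table 2 defines stillbirth as an involuntary loss, so a termination for malformation cannot enter as a stillbirth at any gestational age.

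Elsewhere the protocol seeks exactly these cases:

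- Section 6.1.1.1 collects prenatal test findings, malformations at pregnancy outcome and, in its words, "For elective or therapeutic abortion, reason (e.g., finding on prenatal test" among other reasons.
- Table 2 has the independent evaluator review malformations from any source.
- Section 7.2 says that diagnostic prenatal tests "can determine with high accuracy whether a fetus has a structural or chromosomal abnormality". It treats a woman tested before enrollment as prospective whatever the result, and names a subgroup enrolled after an abnormal test.
- Section 9.2.4 discusses classification bias only for losses in which no MCM was reported.

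For abortions, the Table 3 numerator is "Elective or therapeutic abortions among individuals with pregnancy outcome data" and the denominator is live births. The fetal-loss numerator is "Fetal losses, including SABs, stillbirths, elective or therapeutic abortions, and losses with unknown type, among individuals with pregnancy outcome data", over individuals with pregnancy outcome data.

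**The concern.** Two rules fixed in Table 3 do not fit the rest of the design.

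First, prenatal detection followed by termination is a foreseeable path for a serious malformation, and the program is built to record it. Such a case reaches the adjudicator and is then dropped from both MCM fractions. This works against the sensitivity that the protocol gives as the reason for its convention. Section 1.4 says the results should help patients and physicians weigh risk, so a primary figure of zero alongside a confirmed malformation could mislead them.

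Second, the abortion row stands under a prevalence heading, but its numerator lies wholly outside its denominator. The result is an abortion-to-live-birth ratio, given without explanation. The same abortions have a different denominator in the fetal-loss row.

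**Working it through.** **Inputs.** The fractions come from Section 9.2.2.1 and Table 3, and the expected enrollment of 10 to 20 from Section 9.1. The protocol gives no expected split of outcomes and no expected MCM rate, so there is no planned figure to reproduce. The mixes below are assumptions for illustration: all singleton, all first-trimester exposed, all with known outcome.

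**1. One confirmed MCM, in a terminated pregnancy**

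Assumed mixes, with no stillbirths:

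- N = 10: 7 live births, 1 termination, 2 SABs
- N = 15: 11 live births, 2 terminations, 2 SABs
- N = 20: 15 live births, 2 terminations, 3 SABs

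Formulas:

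- Plan: (MCMs in live births + MCMs in stillbirths) / live births
- A: all MCMs / live births
- B: all MCMs / (live births + stillbirths + terminations)
- C: all MCMs / all known outcomes

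| N | Plan | A | B | C |
|---|---|---|---|---|
| 10 | 0/7 = 0.0% | 1/7 = 14.3% | 1/8 = 12.5% | 1/10 = 10.0% |
| 15 | 0/11 = 0.0% | 1/11 = 9.1% | 1/13 = 7.7% | 1/15 = 6.7% |
| 20 | 0/15 = 0.0% | 1/15 = 6.7% | 1/17 = 5.9% | 1/20 = 5.0% |

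The plan reports zero in every row. Counting the case gives 5.9% to 14.3% under A and B, and 5.0% to 10.0% under C, the widest denominator.

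**2. Elective or therapeutic abortion**

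Plan: abortions / live births. Alternative: abortions / individuals with pregnancy outcome data. For a given count, the plan's figure is larger by the factor (individuals with outcome data) / (live births).

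- 15 pregnancies (9 live births, 1 stillbirth, 2 SABs, 3 abortions): 3/9 = 33.3% against 3/15 = 20.0%; factor 15/9 = 1.67.
- 10 pregnancies (3 live births, 2 SABs, 5 abortions): 5/3 = 166.7% against 5/10 = 50.0%; factor 10/3 = 3.33.

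**3. Stillbirths over live births, for scale**

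If the only MCM is in a stillbirth, the plan gives 1/7 = 14.3% with 7 live births and 1/15 = 6.7% with 15. Adding the stillbirth to the denominator gives 1/8 = 12.5% and 1/16 = 6.3%. The shift is 1.8 and 0.4 percentage points, small beside the effect in step 1.

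**4. Direction of the MCM difference**

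Take the 15-pregnancy mix of step 2, with an MCM in the stillbirth. If one abortion was also for an MCM, the plan gives 1/9 = 11.1% and denominator C gives 2/15 = 13.3%. If no abortion involved an MCM, the plan still gives 11.1% and C gives 1/15 = 6.7%. The plan's figure can lie on either side of the companion.

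**The case against.** The MCM construction is disclosed and sourced, and Section 9.2.2 names the same surveillance system as a source of background rates. Keeping one construction for the study figure and its reference is sensible. That stands, and it supports keeping the figure.

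Terminated cases are absent from one fraction, not from the study. They are adjudicated, they count as serious adverse events under Section 12.1.2, and Section 13.5 has reports include all data received. In so small a program such a case is unlikely to go unseen. That also stands, but it does not make a headline figure of zero a fair summary.

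A companion over all outcomes has its own downward bias, because Section 9.2.4 concedes that the condition of a lost fetus may be unknown. That stands and must be reported with the companion.

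The abortion row is secondary and descriptive, and counts accompany percentages, so a reader could recompute it. Labelling it a ratio would remove the ambiguity, though not the conflict with the fetal-loss row.

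A reader might go further, in three ways that the protocol does not support:

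- That stillbirths over live births is itself an error. It is a declared convention with a small effect.
- That no binomial interval could be applied. The protocol describes none, so this has no bearing on it.
- That the fetal-loss components ought to add to the total. The SAB and stillbirth rows have their own denominators, so the rows would not sum even after the abortion row is changed.

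**Conclusion.** Two points hold, and both should be changed.

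1. Confirmed MCMs in abortions and SABs are missing from both MCM analyses, although the data are collected and adjudicated, and the stated limitations do not mention the omission. With 10 to 20 participants, one case can separate 0% from roughly 5% to 14%, depending on the denominator.
2. The abortion row gives an unexplained ratio that overstates the proportion of pregnancies and has no ceiling at 100%.

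The omissions themselves follow from the text alone. The sizes rest on assumed outcome mixes. A reader might infer that the MCM figure is always biased downward, but step 4 of the working shows that the direction against an all-outcome figure depends on the mix. What is certain is that the numerator drops confirmed cases. Whether the reference surveillance system itself counts terminations cannot be settled from the protocol, and nothing here relies on it.

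**What to change.** Make two changes to Table 3.

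- **MCM.** Keep the present figure for comparison with background rates. Add a prespecified companion row: adjudicated MCMs in any pregnancy outcome, over first-trimester-exposed fetuses with known outcome. Beside it, report how many losses had unknown malformation status. Add a sentence to Section 9.2.4 saying that the present figure omits MCMs reported in abortions and SABs.
- **Elective or therapeutic abortion.** Change the denominator to individuals with pregnancy outcome data, as in the fetal-loss row. If the live-birth version is also wanted, show it separately and label it a ratio.

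The cost is one row, one cell and one sentence, using data already collected. The price in interpretation is that the companion cannot be set directly against live-birth-based background rates and is diluted by unexamined losses, which is why the unknown-status count belongs beside it.
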